### **6.10. Subgroup Analyses**

Subgroup analyses comparing LY3041658 to placebo will be performed on the mITT and PPS population at Week 16 for the following:

- Proportion of participants achieving HiSCR response
- Mean change from baseline to Week 16 in:
  - Total number of abscesses and inflammatory nodules (AN count)
  - Skin Pain – HS Numeric Rating Scale (NRS)

The following subgroups (but not necessarily limited to only these) will be categorized into disease-related characteristics and demographic characteristics will be evaluated:

- Gender: (Male; Female)
- Race: (Asian; Black/African American; White; or Other)
- Ethnicity: (Hispanic or Latino; and Not Hispanic or Latino)
- Region: (United States; and Australia)
- Age (<40,40-65,>65)
- Weight (<60kg, >=60 and <100kg, >=100kg)
- BMI (<25 kg/m^2, >=25 and <40 kg/m^2, >=40 kg/m^2)
- Baseline Hurley stage: II, III

Descriptive statistics will be provided for each treatment and stratum of a subgroup as outlined, regardless of sample size. The subgroup analyses for categorical outcomes will be performed using logistic regression. The model will include the categorical outcome as the dependent variable and treatment, subgroup, and treatment-by-subgroup interaction as explanatory variables. Missing data will be imputed using NRI (Section 6.4). The treatment-by-subgroup interaction comparing treatment groups will be tested at the 0.1 significance level. The p-value

from the logistic regression model will be reported for the interaction test. Response counts and percentages will be summarized by treatment for each subgroup category. The difference in percentages and 100(1-alpha)% confidence interval (CI) of the difference in percentages using the Newcombe-Wilson without continuity correction will be reported. The p-value from the Fisher's exact test will also be produced.

Additional subgroup analyses on efficacy may be performed as deemed appropriate and necessary.

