5.1. Inclusion Criteria

Participants are eligible to be included in the study only if they meet all of the following criteria during the screening period, unless otherwise specified below:

Informed consent

[1] Are capable of giving signed informed consent as described in Appendix 10.1, which includes compliance with the requirements and restrictions listed in the informed consent form (ICF) and in this protocol.

Participant characteristics

[2] Are male or female patients from 18 to 65 years of age (inclusive), at the time of signing the ICF.

Note: Contraceptive use by men or women should be consistent with local regulations regarding the methods of contraception for those participating in clinical studies. Contraception requirements for participants in this study are provided in Appendix 10.4.

HS-related inclusion criteria

- [3] Have a diagnosis of HS for at least 6 months before baseline (the randomization visit).

 Note: a participant with a clinical history of HS may be considered for enrollment if other eligibility criteria are met and if the clinical history is documented by the investigator based on review of the participant's medical history at screening.
- [4] Have HS lesions in at least 2 distinct anatomical regions (for example, right and left axilla; or right axilla and right inguino-crural fold); and at least one of the lesions must be at least Hurley Stage II or Hurley Stage III.
- [5] Have had an inadequate response or intolerance to a 28-day course of oral antibiotics. Examples of inadequate response include the following: any lesion increased in Hurley stage, any lesion requiring intra-lesional steroid injection or incision and drainage, and/or any new anatomic areas developed lesions during the antibiotic course.
- [6] Have a total abscess and inflammatory nodule (AN) count greater than or equal to 4.
- [7] Must agree to use daily, and throughout the duration of the study, one of the following over-the-counter topical antiseptics on body areas affected with HS lesions: chlorhexidine gluconate, triclosan, benzoyl peroxide, or dilute bleach in water.

[8] Are able and willing to comply with the following requirements for use of antibiotics:

If using topical antibiotics for HS at screening, the participant must stop them at least 14 days before baseline (the randomization visit) and must not resume topical antibiotics throughout the duration of the study.

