9.2. Sample Size Determination

Approximately 100 patients will be screened to achieve approximately 63 participants randomized in a 2:1 ratio to one of two treatment groups:

approximately 42 participants randomized to LY3041658, and

approximately 21 participants randomized to placebo.

For all randomized patients, approximately 45 patients are expected to complete the 16 weeks' treatment period. This sample size provides at least 80% power to the primary endpoint of HiSCR response. This calculation is a 2-sided test for superiority of LY3041658 compared to placebo on HiSCR response rate with significance level of 0.05 CCl

CCI

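### The logistic interaction test in SAP 6.10 does not deliver its stated 0.1 level for multi-level or uneven subgroup factors; separately, one listed age level is barred at entry

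*SAP*

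**What the plan says.** SAP 6.10 lists eight subgroup factors for HiSCR at Week 16, analysed on the mITT and the per-protocol set (PPS). Four have two levels: gender, ethnicity, region and Hurley stage. BMI has three levels. The others that matter here are "Race: (Asian; Black/African American; White; or Other"), "Weight (<60kg, >=60 and <100kg, >=100kg") and "Age (<40,40-65,>65").

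For categorical outcomes, "The model will include the categorical outcome as the dependent variable and treatment, subgroup, and treatment-by-subgroup interaction as explanatory variables". The p-value "from the logistic regression model will be reported for the interaction test", and "The treatment-by-subgroup interaction comparing treatment groups will be tested at the 0.1 significance level".

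The section gives descriptive statistics for every stratum whatever its size. It also gives response counts, the difference with a Newcombe-Wilson interval, and a Fisher's exact p-value. Fisher's test is not described as a test of the interaction. There is no merging rule and no minimum size below which the interaction test is dropped.

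Protocol 9.2 plans about 42 participants on active treatment and "approximately 21 participants randomized to placebo". SAP 6.2 still has 34 and 17. Protocol 5.1, criterion 2, reads: "Are male or female patients from 18 to 65 years of age (inclusive), at the time of signing the ICF".

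**The concern.** An ordinary logistic interaction test relies on large-sample theory within each arm-by-level cell. If a cell has no responders or only responders, the interaction term has no finite estimate. The Wald standard error then becomes enormous and the test almost never rejects. The likelihood-ratio statistic stays finite, but its chi-square reference is poor and it rejects too often. About 21 placebo participants spread over three or four levels will often produce such cells.

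At stake is how the reported p-value is read. A reader will take it as a test at 0.1. For race it could be a test at roughly 1% or roughly 15%, depending on which version the software prints, and the SAP does not name one.

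The plan takes small-sample precautions elsewhere. Protocol 9.4.6 allows Fisher's exact test in place of logistic regression for the primary endpoint because the sample is small, and SAP 6.3.3 gives fallbacks if the MMRM does not converge. Neither covers the interaction model, which cuts the same participants into 4 to 8 cells.

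**Working it through.** **The plan's figure.** The 0.1 is a nominal choice with no derivation, so there is nothing to reproduce. The check is whether the test delivers it.

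**Inputs from the documents.** 42 v 21 (Protocol 9.2); 34 v 17 (SAP 6.2); the factor levels and model (SAP 6.10); missing HiSCR counted as nonresponse (SAP 6.4), so treated participants stay in the mITT cells.

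**Assumptions.** The documents give no level shares, and the design HiSCR rates are blacked out. I use 30% v 60% as the base case and then vary it. This is not the design assumption: a pooled two-proportion calculation at 42 v 21, two-sided 0.05, gives power of 0.619 for 30% v 60%, against the stated minimum of 80%.

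**Hand checks on sparsity.**
- A level with 5% prevalence has no placebo participant with probability 0.95^21 = 0.34. At 10% it is 0.90^21 = 0.11.
- The most favourable race split is four equal levels, with 21/4 ≈ 5 placebo participants each. At 30% placebo response one such cell has no responder with probability 0.70^5 = 0.17, and at least one of the four has none with probability 1 − (1 − 0.17)^4 ≈ 0.52. At 25% response the figures are 0.75^5 = 0.24 and about 0.66. Active-arm cells add to this.

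**Simulated size at nominal 0.10.** The SAP model was simulated with no interaction on the logit scale, 2,500 to 4,000 trials per setting for the splits with stated shares. A level empty in either arm was dropped from the degrees of freedom. For Wald, a cell at 0% or 100% was given a logit of ±13 with a correspondingly huge variance, to imitate a fit that stops without converging. Monte Carlo error near 0.10 is about √(0.1 × 0.9/2,500) = 0.006. Ranges are repeat runs.

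| Factor (assumed shares), 42 v 21, 30% v 60% | Wald | Likelihood ratio |
|---|---|---|
| Two levels, 50/50 | 0.076–0.078 | 0.125–0.133 |
| Hurley, 60/40 | 0.072 | 0.127 |
| Age, 60/40 with >65 empty | 0.070 | 0.130 |
| Two levels, 30/70 | 0.059 | 0.137–0.140 |
| Two levels, 85/15 | 0.027–0.029 | 0.142–0.149 |
| Weight, 5/50/45 | 0.040–0.044 | 0.141–0.142 |
| BMI, 15/55/30 | 0.025–0.027 | 0.144–0.153 |
| Race, 5/25/65/5 | 0.012–0.014 | 0.149–0.153 |
| Race, four equal levels | 0.008 | 0.164 |

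A further set of runs at the same sizes and rates gave 0.013 / 0.158 for an uneven race split, 0.024 / 0.159 for BMI and 0.044 / 0.123 for weight.

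In these settings at least one occupied cell had all or no responders in 55% of trials for BMI, 78% for weight and 95% for race (5/25/65/5). A level was empty in at least one arm in 4%, 42% and 67%.

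**Sensitivity.**
- Over 15% v 50%, 30% v 60%, 40% v 70% and 50% v 50%, Wald ran from 0.009 to 0.097 and likelihood ratio from 0.112 to 0.165. A 50/50 factor is nearest nominal at 50% v 50% (0.097 / 0.120) and far from it at 15% v 50% (0.026 / 0.146).
- At the SAP's 34 v 17 and 30% v 60%, Wald ran from 0.015 to 0.064 and likelihood ratio from 0.124 to 0.167.
- The PPS will probably be thinner. If its size is near the 45 expected completers and losses are even, 2:1 leaves 45/3 = 15 on placebo.

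**Control.** At 420 v 210 with a 50/50 factor, the same code gave 0.102 and 0.105, so the departure comes from small cells and not from the simulation.

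**The case against.** These are exploratory subgroup tests in a proof-of-concept trial, with no multiplicity control. Eight independent tests at exactly 0.10 would give at least one false flag with probability 1 − 0.9^8 = 0.57, so strict size is not what anyone relies on. Counts, differences and Newcombe-Wilson intervals by level are already required, so readers will see the thin cells. A better-sized test would also remain weak: an exact conditional mid-p test at 42 v 21, with 60% v 30% in one half and 30% v 30% in the other, rejects at 0.10 only 29% of the time (2,000 runs).

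Most of that stands, and it limits the priority. It does not remove the point, because the SAP still states a level and reports a p-value against it.

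A reader might also infer more than the documents support:
- *That the barred age level distorts the test.* It does not. An unobserved level drops out and leaves <40 against 40–65; the age result (0.070 / 0.130) matches two-level Hurley (0.072 / 0.127).
- *That the 0.1 level is really about 0.01 throughout.* In the base case that describes race under Wald only.
- *That these p-values will misdirect the choice of population for the next study.* Protocol 2.1 speaks of dose selection and benefit/risk, and nothing ties the interaction tests to a population decision.

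**Conclusion.** The concern holds as a minor point. Followed as written, SAP 6.10 misses its stated 0.1 level for race, BMI, weight and any strongly uneven two-level factor. In the base case the size is about 1%, 2% to 3% and 4% by Wald for race, BMI and weight, and about 12% to 16% by likelihood ratio. For balanced two-level factors the gap is smaller, about 7% to 8% by Wald and 13% by likelihood ratio. The direction of the error depends on a choice the SAP does not state.

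The sizes rest on assumed level shares and response rates. The direction was the same across all the rates and splits tried, and for race it appears even with four equal levels.

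The age level above 65 is a separate specification error. With age taken at consent it cannot be filled by an eligible participant, and removing it changes no result. The primary HiSCR comparison is not affected.

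**What to change.** In SAP 6.10:
- Delete the age level above 65.
- Merge race, weight and BMI levels by a written rule to meet a prespecified per-arm minimum (for example 5). The rule should use counts by arm and level only, and be applied without sight of the responses.
- Where a level still falls below the minimum, or a cell has 0% or 100% response, report only the counts, the difference and the Newcombe-Wilson interval, with no interaction p-value.
- Where an interaction p-value is reported, name the test and use a small-sample method. An exact conditional test of equal odds ratios (Zelen, mid-p) and a penalised (Firth) likelihood-ratio test are both reasonable. Label the result exploratory and low-powered.

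Merging is needed as well as a better test. At 42 v 21 and 30% v 60%, the penalised test has size 0.096 (50/50) and 0.088 (30/70) with two levels, but 0.072 for BMI, 0.076 for weight and 0.052 for race with the sparse levels kept. The mid-p test gave 0.06 to 0.11 for the same kinds of factor, under assumed rates of 50% v 25% or 55% v 35%.

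The cost is SAP wording and a standard procedure. The downside is less detail by race, weight and BMI level.

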### **6.11. Protocol Deviations**

Protocol deviations will be tracked by the clinical team, and their importance will be assessed by key team members during protocol deviation review meetings. A list of important protocol deviations (IPDs) will be identified.

Potential examples of deviations include patients who receive excluded concomitant therapy, significant non-compliance with study medication (<80% of assigned doses taken, failure to take study medication and taking incorrect study medication), patients incorrectly enrolled in the study, and patients whose data are questionable due to significant site quality or compliance issues. Refer to a separate document for the important protocol deviations.

The number and percentage of patients having IPD(s) will be summarized within category and subcategory of deviation by treatment group for Period 1 using the mITT population. Individual patient listings of IPDs will be provided.

### **6.12. Interim Analyses and Data Monitoring**

Unblinding details are given in a separate unblinding plan.

Analysis for the primary database lock will be conducted when all participants have completed the Period 1 (or discontinued Period 1 treatment).

There are two interim analyses planned for this study:

1. An interim analysis on unblinded safety data will be triggered when approximately 12 patients have completed 8 weeks of treatment.
2. An interim analysis to assess unblinded efficacy and safety data will be triggered when approximately 21 patients have completed 12 weeks of treatment

Other interim analyses may be conducted as needed. All interim analyses will be used to support planning activities associated with the development program. No adjustment of type I error will be performed.

The assessment will be conducted by an internal assessment committee with a limited number of prespecified team members who do not have direct site contact or data entry/validation responsibilities. A limited number of pre-identified individuals may gain access to the limited unblinded data, as specified in the unblinding plan, prior to the interim or final database lock.

The assessment committee is authorized to evaluate unblinded interim efficacy and safety analyses. Study sites will receive information about interim results ONLY if they need to know for the safety of their patients.

Ongoing monitoring of safety data (including AEs, SAEs, and selected laboratory measurements) will continue throughout the study using blinded data. Interim safety analyses may be conducted to review unblinded safety data. The analyses will be conducted and reviewed by an internal assessment committee composed of personnel who do not have direct site contact or data entry/validation responsibilities.

Details of the planned interim data analyses and the assessment committee data review process are included in an assessment committee charter.

### **6.13. Annual Report Analyses**

Annual report analyses, such as the Development Update Safety Report (DSUR), will be documented in a separate document.

### **6.14. Clinical Trial Registry Analyses**

Additional analyses will be performed for the purpose of fulfilling the Clinical Trial Registry (CTR) requirements.

Analyses provided for the CTR requirements include a summary of AEs, provided as a dataset which will be converted to an XML file. Both SAEs and ‘Other’ AE are summarized: by treatment group, by MedDRA PT.

- An AE is considered ‘Serious’ whether or not it is a TEAE.
- An AE is considered in the ‘Other’ category if it is both a TEAE and is not serious. For each SAE and ‘Other’ AE, for each term and treatment group, the following are provided:
  - the number of participants at risk of an event
  - the number of participants who experienced each event term
  - the number of events experienced.
- Consistent with [www.ClinicalTrials.gov](http://www.ClinicalTrials.gov) requirements, ‘Other’ AEs that occur in fewer than 5% of patients/patients in every treatment group may not be included if a 5% threshold is chosen (5% is the minimum threshold).
- AE reporting is consistent with other document disclosures for example, the CSR, manuscripts, and so forth.

Similar methods will be used to satisfy the European Clinical Trials Database (EudraCT) requirements.

## 8. Appendices

---

**Appendix 1. Lilly-Defined MedDRA Preferred Terms for Herpes Zoster**

---

Preferred Term (MedDRA Version 18.0)	Preferred Term Code
Herpes zoster	10019974
Ophthalmic herpes zoster	10030865
Herpes zoster infection neurological	10061208
Herpes zoster oticus	10063491
Herpes zoster disseminated	10065038
Genital herpes zoster	10072210
Herpes zoster pharyngitis	10074245
Herpes zoster meningoencephalitis	10074248
Herpes zoster meningomyelitis	10074251
Herpes zoster meningitis	10074259
Herpes zoster cutaneous disseminated	10074297
Varicella zoster virus infection	10075611

---

**Appendix 2. Lilly-Defined MedDRA Preferred Terms for Tuberculosis**

---

Preferred Term (MedDRA Version 18.0)	Preferred Term Code
Adrenal gland tuberculosis	10001358
Bone tuberculosis	10056377
Bovine tuberculosis	10006049
Choroid tubercles	10008779
Congenital tuberculosis	10010657
Conjunctivitis tuberculous	10010754
Cutaneous tuberculosis	10011684
Disseminated tuberculosis	10013453
Ear tuberculosis	10014027
Epididymitis tuberculous	10015004
Erythema induratum	10015213
Extrapulmonary tuberculosis	10064445
Female genital tract tuberculosis	10061150
Immune reconstitution inflammatory syndrome associated tuberculosis	10072797
Interferon gamma release assay positive	10072866
Intestinal tuberculosis	10075268
Joint tuberculosis	10056367
Latent tuberculosis	10065048
Lupus vulgaris	10025143
Lymph node tuberculosis	10025183
Male genital tract tuberculosis	10061234
Meningitis tuberculosis	10027259
Mycobacterium tuberculosis complex test positive	10070325
Oesophageal tuberculosis	10030200
Pericarditis tuberculous	10055069
Peritoneal tuberculosis	10053583
Prostatitis tuberculous	10064743
Pulmonary tuberculoma	10066927
Pulmonary tuberculosis	10037440
Renal tuberculosis	10038534
Salpingitis tuberculous	10039463
Silicotuberculosis	10068876
Spleen tuberculosis	10041640
Thyroid tuberculosis	10043774
Tuberculin test positive	10044728
Tuberculoma of central nervous system	10052883
Tuberculosis	10044755
Tuberculous abscess central nervous system	10052884
Tuberculosis bladder	10044758
Tuberculosis gastrointestinal	10061390

Preferred Term (MedDRA Version 18.0)	Preferred Term Code
Tuberculosis liver	10058120
Tuberculosis of central nervous system	10061391
Tuberculosis of eye	10044819
Tuberculosis of genitourinary system	10044828
Tuberculosis of intrathoracic lymph nodes	10044846
Tuberculosis of peripheral lymph nodes	10044965
Tuberculosis ureter	10045026
Tuberculous endometritis	10071559
Tuberculous laryngitis	10045072
Tuberculous pleurisy	10045104
Tuberculous tenosynovitis	10059161

### Appendix 3. Lilly-Defined MedDRA Preferred Terms for Potential Opportunistic Infections

Preferred Term (MedDRA Version 18.0)	Preferred Term Code
Candida pneumonia	10053158
Respiratory moniliasis	10038705
Gastrointestinal candidiasis	10017938
Oesophageal candidiasis	10030154
Coccidioides encephalitis	10054214
Coccidioidomycosis	10009825
Cutaneous coccidioidomycosis	10068747
Meningitis coccidioides	10027207
Cryptococcal cutaneous infection	10054216
Cryptococcal fungaemia	10067112
Disseminated cryptococcosis	10013439
Gastroenteritis cryptococcal	10011485
Meningitis cryptococcal	10027209
Neurocryptococcosis	10068368
Biliary tract infection cryptosporidial	10067319
Gastroenteritis cryptosporidial	10017899
Cytomegalovirus colitis	10048983
Cytomegalovirus duodenitis	10049014
Cytomegalovirus enteritis	10049074
Cytomegalovirus enterocolitis	10049015
Cytomegalovirus gastritis	10049016
Cytomegalovirus gastroenteritis	10051349
Cytomegalovirus gastrointestinal infection	10052817
Cytomegalovirus gastrointestinal ulcer	10075619
Cytomegalovirus hepatitis	10011830
Cytomegalovirus mucocutaneous ulcer	10065036
Cytomegalovirus myelomeningoradiculitis	10065621
Cytomegalovirus myocarditis	10056261
Cytomegalovirus oesophagitis	10049018
Cytomegalovirus pancreatitis	10049566
Cytomegalovirus pericarditis	10056721
Cytomegalovirus proctocolitis	10049019
Cytomegalovirus urinary tract infection	10051350
Disseminated cytomegaloviral infection	10049075
Encephalitis cytomegalovirus	10014586
